3.2.1 Potential Risks

(Please refer to tofacitinib package insert for complete risk profile)

Study Drug (Tofacitinib) Risks

Like all medicines, this medicine can cause side effects, although not everybody gets them.

Very common side effects (these may affect 1 in 10 people or more, or >10%): none.

Common side effects (these may affect up to 1 in 10 people, or up to 10%): upper respiratory tract infection (nasopharyngitis, common cold), lung infection (pneumonia and bronchitis), shingles (herpes zoster), influenza (flu), sinusitis, urinary bladder infection (cystitis), sore throat (pharyngitis), increased muscle enzymes or cholesterol, weight gain, stomach (belly) pain (which may be from inflammation of the stomach lining), vomiting, diarrhea, nausea, indigestion, pain in the joints, low red blood cell count (anemia), fever, fatigue (tiredness), swelling of the feet and hands, headache, high blood pressure (hypertension), cough, rash.

Uncommon side effects (these may affect up to 1 in 100 people, or up to 1%): tuberculosis, kidney infection, viral infections, skin infection, herpes simplex or cold sores (oral herpes), viral infections affecting the gut, increased liver enzymes, low white blood cell count, blood creatinine increased (a possible sign of decreased kidney function), dehydration, pain in the muscles, muscle strain, tendonitis, joint swelling, ligament sprain, abnormal sensations, poor sleep, shortness of breath or difficulty breathing, sinus congestion, skin redness, itching, fatty liver, inflammation of outpouchings of your intestine (diverticulitis), tears in your stomach or intestines, some types of skin cancers (nonmelanoma-types), drug allergy (which can involve bumpy skin rash, swelling around lips and tongue, wheezing, dizziness or lightheadedness).

Rare side effects (these may affect up to 1 in 1,000 people, or up to 0.1%): blood infection (sepsis), joint infection, tuberculosis involving the brain and spinal cord, bones and other organs, and other unusual infections.

EMERGING SAFETY INFORMATION - MORTALITY

In one ongoing study in rheumatoid arthritis patients who were 50 years of age or older with at least one risk factor for heart disease, patients treated with tofacitinib 10 mg twice a day

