had a higher frequency of mortality (death), compared to patients treated with tofacitinib 5 mg twice a day or a tumor necrosis factor inhibitor medication (adalimumab or etanercept). In patients treated with tofacitinib 10 mg twice a day in other tofacitinib studies, the frequency of death has not been higher than the frequency of death in patients treated with tofacitinib 5 mg twice a day.

Minimizing risks: Patients will be evaluated at least once daily, depending on the level of care required of their overall condition after treatment initiation.

Toxicity monitoring: Patients will be monitored at least once daily after initiation of therapy, depending on the level of care required of their overall condition. On each day an H&P will be performed and the patient will undergo laboratory monitoring including hsCRP, ferritin, LDH, D-dimer, CBC, and CMP (SOC). If there is suspected toxicity from the therapy, the dose of tofacitinib may be reduced to 5 mg BID or stopped entirely, depending on the toxicity observed or suspected.

Research blood samples: The results of the research testing will not appear in the subject's medical file. No individual identifiers will be used for any testing. All samples and data are given a unique code to remove any identifying information. Any information that identifies the subject will be kept separate from the samples and this identified information will be kept until the study is complete.

With respect to prophylactic management of VTE, we will follow the institutional standard of care algorithm at the time of the study (**Appendix 1**).

Risk Mitigation Strategies

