5.3.2 Eligibility Criteria/Vulnerable Populations

Inclusion Criteria:

Participants are eligible to be included in the study only if all of the following criteria apply:

Age and Sex:

Male or female participants between the ages of 18 and 99 years, inclusive, at screening. Refer to **Appendix 3** for contraceptive guidance for participants.

Type of Participant and Disease Characteristics:

- 1. Participants who are willing and able to comply with all scheduled visits, treatment plan, laboratory tests, lifestyle considerations, and other study procedures.
- 2. Participants with laboratory-confirmed novel coronavirus (SARS-CoV-2) infection as determined by polymerase chain reaction (PCR) or other commercially available or public health assay prior to Day 1.

- Participants with evidence of pneumonia assessed by radiographic imaging (chest x-ray or chest CT scan) AND Requiring ≥ 3L O2 OR ≥ 2L O2 and hsCRP > 70 mg/L
- 4. Participants who are hospitalized and receiving supportive care for COVID-19.

Informed Consent:

Participant (or legally authorized representative/surrogate) capable of giving signed informed consent.

Exclusion Criteria:

Participants are excluded from the study if any of the following criteria apply:

Medical Conditions:

- 1. Require mechanical ventilation or ECMO on Day 1 at the time of randomization.
- 2. Have current, or history of, venous thromboembolism (deep vein thrombosis or pulmonary embolism).
- 3. Have a personal or first-degree family history of blood clotting disorders.
- 4. Participants who are immunocompromised, with known immunodeficiencies, or taking potent immunosuppressive agents (eg, azathioprine, cyclosporine).
- 5. Participants with any current malignancy or lymphoproliferative disorders that requires active treatment
- 6. Females of child bearing potential who are pregnant or breastfeeding
- 7. Other medical or psychiatric condition including recent (within the past year) or active suicidal ideation/behavior or laboratory abnormality that may increase the risk associated with study participation or, in the investigator's judgment, make the participant inappropriate for the study.
- 8. Anticipated survival < 72 hours as assessed by the Investigator.

Infection History:

- Suspected or known active systemic bacterial, fungal, or viral infections (with the exception of COVID-19) including but not limited to:
 - Secondary bacterial pneumonia;
 - Active herpes zoster infection;

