 - Known active tuberculosis or history of inadequately treated tuberculosis;
 - Known HBV, HCV, or HIV.

Prior/Concomitant Therapy:

Have received any of the following treatment regimens specified in the timeframes outlined below:

Within 4 weeks prior to the first dose of study intervention:

- Prior treatment with any JAK inhibitors, potent immunosuppressants, or any biologic agents including IL-6 inhibitors (eg, tocilizumab) or IL-1 inhibitors (eg, anakinra) within the past 28 days or 5 half-lives, whichever is longer.
- Prior treatment with any potent cytochrome P450 inducer, such as rifampin, within the past 28 days or 5 half-lives, whichever is longer.

Within 48 hours prior to the first dose of study intervention:

• Treatment with herbal supplements.

Received >/= 20 mg/day of prednisone or equivalent for >/=14 consecutive days in the 4 weeks prior to screening

Diagnostic Assessments:

- Severe hepatic impairment, defined as Child-Pugh class C.
- Severe anemia (hemoglobin <8 g/dL).
- ANY of the following abnormalities in clinical laboratory tests at screening, confirmed by a single repeat, if deemed necessary:
 - WBC <1000/mm3
 - Absolute lymphocyte count <500 cells/mm³;
 - Absolute neutrophil count <1000 cells/mm³.
- Alanine transaminase/aspartate transaminase (ALT/AST) > 5 times the upper limit of normal;
- Estimated glomerular filtration rate (eGFR) < 40 mL/min/1.73 m2);

Other Exclusions:

- Known allergy to tofacitinib.
- Investigator site staff or Pfizer employees directly involved in the conduct of the study, site staff otherwise supervised by the investigator, and their respective family members.
- Enrollment in another clinical trial to study COVID-19

Treatment Considerations

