Based on the above discussion, there appears to be a meaningful dose-dependent difference in effect on inflammation favoring the higher dose whereas there is no apparent short-term, dose-dependent risk increase for thrombosis. Taken together, in combination with the appropriate risk minimization measures, the benefit/risk is considered more favorable with tofacitinib 10 mg BID relative to 5 mg BID and the higher dose is therefore suggested as appropriate for evaluation in COVID-19 patients. Specifically, the following rationale supports evaluation of 10 mg BID:

- At the 10 mg BID dose, plasma tofacitinib concentrations are maintained above the IC50 for IL-6 inhibition throughout a 24-hour dosing interval at steady-state, unlike the lower dose of 5 mg BID. Along with other PD data discussed, the 10 mg BID dose provides better anti-inflammatory effects, than 5 mg BID, for controlling potential increase in cytokines and progression to ARDS.
- Tofacitinib 5 and 10 mg BID have been extensively studied in RA, PsA and UC clinical development programs and the short-term and long-term safety profile of tofacitinib 10 mg BID is well characterized.
- Tofacitinib 10 mg BID is the approved dose in the EU and globally for induction therapy up to 16 weeks in UC patients with potential for longer term use if needed for maintenance of treatment benefit.
- Short-term exposure to tofacitinib 10 mg BID has not been associated with an increased risk of thrombosis (either arterial or venous) when compared to 5 mg BID and time to first reported thrombotic event in patients treated with tofacitinib 10 mg BID was 72 days and 216 days in RA and UC patients, respectively.
 - Protocol risk minimization measures include:
 - Patients with severe hearth failure (NYHA 3 or 4), history of recurrent DVT or PE are excluded per protocol.
 - In pooled RA studies, there were no events reported during the first 3 months of tofacitinib 5 mg BID or 10 mg BID treatment in patients who did not have baseline VTE risk factors such as previous VTE, previous heart failure, or age ≥60 years.
 - All patients will receive Low Molecular Weight Heparin subcutaneously at prophylactic dosage.
- Therefore, the benefit/risk of short duration treatment appears more favorable with tofacitinib 10 mg BID relative to 5 mg BID for the control of potential hyperinflammation in COVID-19 and the use of 10 mg BID appears to be justified based on currently available information.

9 References

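### Appendix 4 counts exclusion of NYHA 3–4 heart failure as a safeguard for 10 mg BID, but section 5.3.2 has no heart-failure criterion

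*Protocol*

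**What the plan says.** Appendix 4 of the protocol compares 10 mg with 5 mg BID and concludes that, "in combination with the appropriate risk minimization measures, the benefit/risk is considered more favorable with tofacitinib 10 mg BID" relative to the lower dose. Its list of protocol measures includes the sentence "Patients with severe hearth failure (NYHA 3 or 4), history of recurrent DVT or PE are excluded per protocol". The risk-mitigation table in section 3.2.1 makes a broader statement of the same kind: that the eligibility criteria keep out people with risk factors for VTE.

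The operative rules are in section 5.3.2. Exclusion 2 covers thrombosis: "Have current, or history of, venous thromboembolism (deep vein thrombosis or pulmonary embolism". Exclusion 3 covers personal or first-degree family clotting disorders. Exclusion 7 is general. It covers other medical or psychiatric conditions, or laboratory abnormalities, "that may increase the risk associated with study participation or, in the investigator's judgment, make the participant inappropriate for the study". Where section 5.3.2 wants a fixed limit on organ function it gives one, for example "Severe hepatic impairment, defined as Child-Pugh class C", ALT/AST above 5 times the upper limit of normal, or eGFR below 40.

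On baseline reporting, protocol 6.5.5 plans summaries of demographics and medical history by arm. Screening (protocol 6.3.3) collects age and comorbidities. SAP 6.4.1 lists the baseline summaries, and neither age nor medical history is among them.

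**The concern.** A dose rationale that cites an exclusion as being in the protocol should be matched by a criterion that screening staff can apply. Here the rationale names a condition and a severity class, and the criteria name neither.

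Heart failure is relevant to the argument Appendix 4 makes. That argument is about thrombosis. It treats previous heart failure as a baseline VTE risk factor, and it reports that in pooled RA data over months 0 to 3 no thrombotic events occurred at either dose in patients without such factors. If patients with severe heart failure can enter the trial, that statement need not describe everyone dosed. A reader of the benefit/risk section would believe that a group at raised thrombotic risk had been kept out by rule, when its exclusion depended on a general clause.

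The baseline tables are a separate and smaller matter. As SAP 6.4.1 is written, they would not show how many participants had a history of heart failure, or how old participants were.

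**Working it through.** No figure in the plan needs to be reproduced; the check compares texts.

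**1. Appendix 4 against section 5.3.2**

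| Appendix 4 says is excluded | Section 5.3.2 | Match |
|---|---|---|
| Recurrent DVT or PE | Exclusion 2: any current or past DVT or PE | Yes, and stricter |
| Heart failure, NYHA 3 or 4 | No criterion names heart failure or NYHA class; exclusion 7 may reach it | Not as a named rule |

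One of the two exclusions in the sentence is a named criterion. The numbered medical exclusions run from 1 to 8 without a break, so there is no sign that a criterion was lost when the text was extracted.

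**2. The mitigation table against section 5.3.2**

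The note to the thrombosis figure in Appendix 4 defines a VTE risk factor as any of: oral contraceptive or hormone replacement use, previous heart failure, previous VTE, age 60 or over, BMI 30 or over, smoking, antidepressant use or aspirin use. Of these, only previous VTE is a named exclusion in section 5.3.2. Age is admitted up to 99, and hormonal contraceptives are expressly allowed. The table's general statement in section 3.2.1 is therefore true for VTE history and clotting disorders, but not for risk factors as Appendix 4 defines them.

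**3. What the dose argument rests on without the heart-failure exclusion**

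- Any VTE history is excluded (section 5.3.2).
- LMWH prophylaxis is mandatory (sections 5.3.2 and 6.1.11).
- Treatment stops on a diagnosis of thrombosis (sections 6.1.2 and 6.3.7).
- Treatment lasts no more than 14 days (section 6.3.5). In completed RA and UC studies at 10 mg BID no thrombotic event occurred in the first 14 days; the earliest were at day 72 (RA) and day 216 (UC) (Appendix 4).

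The 14-day statement is not limited to patients without heart failure, so it does not depend on the missing criterion. The month 0–3 statement about patients without risk factors does.

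**4. Baseline summaries**

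SAP 6.4.1 lists gender, race, ethnicity, NIAID score, PT/PTT, days since symptom onset, days since diagnosis, fibrinogen, D-dimer, hs-CRP, ferritin, procalcitonin, LDH, tobacco history, height and weight: 16 items, with neither age nor medical history. SAP 6.4.4 covers treatments only, and SAP 6.3 marks subset analyses as not applicable. SAP 2.1 declares one change to the protocol's analysis, the removal of hypothesis testing. The omission from the list is therefore not declared.

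**The case against.** The strongest reply is that exclusion 7 already does the work. Its first limb covers a medical condition that may raise the risk of taking part, and the protocol itself classes heart failure as a VTE risk factor. An investigator could properly exclude NYHA 3–4 heart failure under it. This stands as far as it goes: section 5.3.2 does not compel entry of such patients. But a general clause without a threshold is not the NYHA 3–4 rule that Appendix 4 describes, and two investigators could apply it differently.

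A second reply is that the dose conclusion hardly depends on this sentence. That is largely right, given the other supports, and it is why the point is small.

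A third is that enrolment has ended (SAP 2.3 and 7) and the analysis is descriptive, so an eligibility change can protect no one now. Also right; what remains is the accuracy of the written rationale and of the report.

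A fourth concerns the SAP list. Protocol 6.5 lets the SAP modify the analysis, and SAP 2.0 was written for an abbreviated report. One may also argue that protocol 6.5.5 was never withdrawn and still applies. So the omission is not a breach. It leaves unclear whether the summaries will appear.

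A reader might go further and link the gap to the mortality signal in section 3.2.1, where "rheumatoid arthritis patients who were 50 years of age or older with at least one risk factor for heart disease" on 10 mg twice daily "had a higher frequency of mortality (death), compared to patients treated with tofacitinib 5 mg twice a day". The documents do not support that link for this point. The signal comes from RA, and a risk factor for heart disease is not heart failure. The same section adds: "In patients treated with tofacitinib 10 mg twice a day in other tofacitinib studies, the frequency of death has not been higher" than at 5 mg. Appendix 4 brings in heart failure through thrombosis, and the concern should rest there.

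**Conclusion.** The point holds in a limited form. Appendix 4 states as a protocol safeguard an exclusion that section 5.3.2 does not contain as a named criterion, and the mitigation table in section 3.2.1 overstates how far eligibility removes VTE risk factors. The severity is low minor.

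The size cannot be put in participants. The documents do not say how many enrolled patients had heart failure, and screening does not specify that NYHA class be recorded. Nothing shows that a patient with severe heart failure was enrolled or harmed. Nor does the gap overturn the choice of 10 mg BID, whose other supports are intact. Either inference would go beyond the documents.

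The conclusion assumes that section 5.3.2 is the complete list of criteria, and that no separate screening instruction, unseen here, applied an NYHA limit. The missing age and medical-history summaries are real, but secondary and separate.

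**What to change.** **Eligibility.** Add *NYHA class 3 or 4 heart failure* to the section 5.3.2 exclusions. During enrolment this would have cost one line and slightly fewer eligible patients. As enrolment has ended, correct the Appendix 4 sentence to say that any VTE history is excluded and that severe heart failure is left to exclusion 7. If the protocol will not be amended again, say in the study report that heart failure was not applied as a named exclusion. The section 3.2.1 table should be narrowed in the same way, to VTE history and clotting disorders.

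**Reporting (secondary).** Add age and medical history, including heart failure, by arm to SAP 6.4.1. Both come from data collected at screening under protocol 6.3.3, so the cost is two baseline blocks and no new data. The summary can show a history of heart failure but probably not its NYHA class. The age summary would also show the actual range, which is useful because SAP 2.3 describes the population as 18–65 and the protocol as 18–99.

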## 1. VERSION HISTORY

### SUMMARY OF CHANGES

SAP Version	Change	Rationale
2.0	Hypothesis testing for treatment comparison will not be conducted. Only descriptive analyses will be generated.	The study concluded prematurely with a smaller-than-anticipated participant cohort, attributed to the return to pre-pandemic conditions as COVID-related restrictions eased during the recruitment phase. The abbreviated CSR is intended to be reported for this study (as per DMB10-GSOP), the changes in statistical reporting modification have been implemented.
1.0	Not Applicable	Not Applicable

## 2. INTRODUCTION

This SAP provides the detailed methodology for summary and statistical analyses of the data collected in Study 2000027848.

Statistical Analysis Plan (SAP) has been developed in response to the challenges posed by the COVID-19 pandemic, which led to a lower-than-anticipated recruitment of patients and the premature conclusion of the study. As a result, the estimands outlined in this version primarily focus on descriptive methods rather than comparative analysis between treatment groups. This document provides a comprehensive overview of the updated methodology for summarizing and analyzing the data collected in Study 2000027848, considering the modifications necessitated by the unique circumstances of the pandemic.

### 2.1. Modifications to the Analysis Plan Described in the Protocol

As rationalized above, no hypotheses testing for treatment comparison will be done, only descriptive analysis will be done by the treatment groups.

### 2.2. Study Objectives, Endpoints, and Estimands

Objectives/ Endpoints	Type of Endpoints [categorical (including binary), continuous, or time to endpoints]
Primary	
The primary objective of this study is to determine whether tofacitinib improves the clinical outcomes of patients with moderate SARS-CoV-2 infection as determined by the Primary outcome measure.	Binary endpoint

Endpoint: Proportion of subjects alive and not needing any form of mechanical ventilation, high flow oxygen, or ECMO by day 14 and day 30.	
Secondary	
Clinical improvement (defined as a 2-point increase) as measured by NIAID 8-point ordinal scale (i.e., 1 = death and 8 = Not hospitalized, no limitations on activities) at day 14.	Categorical endpoint
Clinical status using ordinal scale (days 3 through day 14): The ordinal scale is an assessment of the clinical status at the first assessment of a given study day. The scale is as follows: 1) Death; 2) Hospitalized, on invasive mechanical ventilation or extracorporeal membrane oxygenation (ECMO); 3) Hospitalized, on non-invasive ventilation or high flow oxygen devices; 4) Hospitalized, requiring supplemental oxygen; 5) Hospitalized, not requiring supplemental oxygen - requiring ongoing medical care (COVID-19 related or otherwise); 6) Hospitalized, not requiring supplemental oxygen - no longer requires ongoing medical care; 7) Not hospitalized, limitation on activities and/or requiring home oxygen; 8) Not hospitalized, no limitations on activities.	Categorical endpoint
Time to recovery (Day of recovery is defined as the first day on which the subject satisfies one of the following three categories from the clinical status of ordinal scale: 6) Hospitalized, not requiring supplemental oxygen - no longer requires ongoing medical care; 7) Not hospitalized, limitation on activities and/or requiring home oxygen; 8) Not hospitalized, no limitations on activities) through day 14 and day 30 from day 1.	Time to endpoint.
Time to clinical improvement (defined as a 2-point increase on the ordinal scale).	Time to endpoint
Clinical status on ordinal scale at day 30, 60, and 90.	Categorical endpoint
Mortality rate at day 30, 60 and 90.	Binary endpoint
Proportion of patients requiring ICU admission and mechanical ventilatory support (defined as clinical status of 2 and hospitalization status = ICU) at 14 and 30 days.	Binary endpoint
Change from Baseline in inflammatory parameters (eg. hsCRP, procalcitonin, ferritin, D-dimers, LDH, fibrinogen, PT/PTT).	Continuous endpoint
Change from baseline in cytokines (e.g. IL-1, IL-2, IL-6, IL-8, TNF- $\alpha$ , IL-17A, IL-17F, IP-10, CCL5), as available	Continuous endpoint
Safety as assessed by reporting of adverse events, changes in clinical laboratory parameters (e.g., hemoglobin, hepatic transaminases, serum creatinine, bilirubin, and evidence of secondary infections)  Safety Endpoints: Adverse events:	

 
Incidence of treatment emergent adverse events (TEAE), serious adverse events, AEs leading to discontinuation.
 
	Binary endpoint

Laboratory data
 
 
Change from baseline clinical laboratory parameters.
 
Incidence of clinically significant abnormalities in laboratory parameters.
 
	Continuous endpoint Binary endpoint

Vital signs
 
 
incidence of clinically significant abnormalities in vital signs
 
	Binary endpoint

Electrocardiogram
 
 
Changes from baseline for the ECG parameters
 
Incidence of clinically significant abnormalities in ECG results
 
	Continuous endpoint Binary endpoint
Intervention with additional immunomodulatory agent (i.e. IL-6 targeting therapy)	Binary endpoint
Change in SARS-CoV-2 viral titers during intervention	Continuous endpoint

